5.1. Consent Process

5.1.1. Obtaining Informed Consent

1. Timing and Location of Consent

When participants attend their first in person visit, they will have the study explained to them in detail, have the opportunity to ask questions and then be asked to sign the consent form. Participants will be given a signed copy of

the form. This will take place in a private clinic room at the Penn State Hershey Clinical Research Center.

2. Coercion or Undue Influence during Consent

Recruitment materials for the study will be broadly distributed throughout the community. Once participants contact the study center, they will be given information about the study and offered the opportunity to participate. The researchers obtaining consent will be instructed to clearly indicate that the participant's enrollment in the trial is purely voluntary and the researchers will not offer comments about whether they believe the participant should enroll in the study or not. Given the number of contacts and visits involved in the study protocol, the compensation provided to the participant is modest.

5.1.2. Waiver or alteration of the informed consent requirement

N/A

5.2. Consent Documentation

5.2.1. Written Documentation of Consent

An IRB approved, stamped consent form will be used to document consent. Both the researcher and the participant will retain a copy of the consent.

5.2.2. Waiver of Documentation of Consent

Participants who are interested in the study will be asked to consent to allow the researcher to pre-screen them for the study over the phone by asking all screening questions of all participants (eligible or ineligible). Participants will be asked if this information can be retained so that the study team will know reasons that participants are not eligible for the study.

Participants who are not eligible for the study, or those who begin the phone screeners but are not interested in completing it after learning more about the study, will be asked if they would be interested in being contacted for future studies being conducted by our research team. They will be informed that by providing their name and phone number, they will be consenting to allow the study team to contact them in the future.

5.3. Consent – Other Considerations

5.3.1. Non-English Speaking Subjects

Non-English speaking subjects will not be eligible for this study because it is essential for assessing their experience with the protocol during study contacts (i.e. telephone interviews) and some of our measures are not validated in other languages.

5.3.2. Cognitively Impaired Adults

Cognitively impaired adults will not be eligible for this study.

1. Capability of Providing Consent

N/A

2. Adults Unable To Consent

N/A

3. Assent

N/A

5.3.3. Subjects who are not yet adults (infants, children, teenagers)

Children will not be eligible for this study.

1. Parental Permission

N/A

2. Assent

N/A

6. HIPAA Research Authorization and/or Waiver or Alteration of Authorization

6.1. Authorization and/or Waiver or Alteration of Authorization for the Uses and Disclosures of PHI

Check all that apply:

- Authorization will be obtained and documented as part of the consent process.
- Partial waiver is requested for recruitment purposes only (*Check this box if patients' medical records will be accessed to determine eligibility before consent/authorization has been obtained*)
- Full waiver is requested for entire research study (e.g., *medical record review studies*)
- Alteration is requested to waive requirement for written documentation of authorization

6.2. Waiver or Alteration of Authorization for the Uses and Disclosures of PHI

6.2.1. Access, use or disclosure of PHI representing no more than a minimal risk to the privacy of the individual

1. Plan to protect PHI from improper use or disclosure

All data collected during the screening process will be directly entered into REDCap.

2. Plan to destroy identifiers or a justification for retaining identifiers

All study data will be retained indefinitely.

6.2.2. Explanation for why the research could not be practicably be conducted without access to and use of PHI

N/A

6.2.3. Explanation for why the research could not practicably be conducted without the waiver or alteration of authorization

In order to screen the participants prior to inviting them into the study center, the investigators are conducting a phone screen to determine if the participants are likely to be eligible in the study.

6.3. Waiver or alteration of authorization statements of agreement

Protected health information obtained as part of this research will not be reused or disclosed to any other person or entity, except as required by law, for authorized oversight of the research study, or for other permitted uses and disclosures according to federal regulations.

The research team will collect only information essential to the study and in accord with the 'Minimum Necessary' standard (information reasonably necessary to accomplish the objectives of the research) per federal regulations.

Access to the information will be limited, to the greatest extent possible, within the research team.

All disclosures or releases of identifiable information granted under this waiver will be accounted for and documented.

7. Study Design and Procedures

7.1. Study Design

This will be a two-arm randomized double-blinded trial. The study will proceed in four phases.

1. In Baseline Phase 1, subjects will smoke their own usual brand of cigarettes for 1 week to get acclimated to study participation.
2. In Baseline Phase 2, participants will be assigned (unblinded) to use research cigarettes that contain the normal amount of nicotine of conventional store bought cigarettes and matched on the participants' menthol flavor preference (menthol or non-menthol) for 2 weeks. Participants who complete this 2 week period of smoking research cigarettes and agree to continue with the study will enter the Randomized Double-Blind Phase.
3. During Randomization Phase 3, participants will be randomized to either:
 - a. continue to smoke the same research cigarettes for a further 18 weeks
 - b. switch to progressively reduced nicotine content (RNC) cigarettes over the next 18 weeks
4. Finally, during Treatment Choice Phase 4, both groups will then be offered the choice to:
 - a. return to their usual brand
 - b. Receive assistance to quit smoking (with counseling and FDA-approved medication provided at no cost for 11 weeks)

Table 1: Dosing Schedule for smokers enrolled in the study prior to 12/19/16

Phase:	Baseline I	Baseline II	Randomized Double-Blind Phase					Treatment Choice Phase**
Wks/Phase:	1	2	3	3	3	3	6	12
Cigarette type:	Own Brand	Usual Nicotine Research Cigarettes	Reduced Nicotine Step 1	Reduced Nicotine Step 2	Reduced Nicotine Step 3	Reduced Nicotine Step 4	Reduced Nicotine Step 5	Variable
Nicotine content (mg/cigarette)[†]								
regular: RNC	Around 11mg	11.0	7.8	3.2	1.3	0.7	0.2	Variable
		12.1	7.0	3.4	1.4	0.7	0.2	
regular: UNC	Around 11mg	11.0	11.0	11.0	11.0	11.0	11.0	Variable*
		12.1	12.1	12.1	12.1	12.1	12.1	

*Menthol smokers randomized to the UNC treatment group who choose to stay on study cigarettes will switch to a 9.9 mg or 12.1 mg cigarette type determined by the time of entry into the study due to a 12.1 mg menthol study cigarette supply shortage. A consent form addendum will be filled out for all menthol smokers who choose to stay on study cigarettes in the Treatment Choice Phase.

Table 2: Dosing Schedule for smokers enrolled 12/19/16 or after

Phase:	Baseline I	Baseline II	Randomized Double-Blind Phase					Treatment Choice Phase**
Wks/Phase:	1	2	3	3	3	3	6	12
Cigarette type:	Own Brand	Usual Nicotine Research Cigarettes	Reduced Nicotine Step 1	Reduced Nicotine Step 2	Reduced Nicotine Step 3	Reduced Nicotine Step 4	Reduced Nicotine Step 5	Variable
Nicotine content (mg/cigarette)[†]								
regular: RNC	Around 11mg	11.0	7.8	3.2	1.3	0.7	0.2	Variable
		9.9	7.0	3.4	1.4	0.7	0.2	
regular: UNC	Around 11mg	11.0	11.0	11.0	11.0	11.0	11.0	Variable
		9.9	9.9	9.9	9.9	9.9	9.9	

**As of the approval date of the June 7th 2017 version of the protocol, smokers entering the treatment choice phase will not be given the option to stay on research cigarettes.

[†]Nicotine contents are based on an estimated 0.7 g tobacco content per cigarette and nicotine concentrations (mg/g) from Richter et al. (2016)[36]

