Another research group conducted three studies using reduced nicotine content cigarettes. The three studies were: 1) a single cigarette crossover, comparing cigarettes of different nicotine content and yield; 2) a 6 week tapering study, where nicotine yields were decreased on a weekly basis; 3) a similar tapering study in which nicotine yields were decreased on a monthly basis. All studies found: 1) Systemic intake of nicotine reflected the nicotine content of the cigarettes, with only small degrees of compensation. That is, as nicotine content declined, nicotine intake declined proportionally; 2) No evidence of increased systemic exposure to carcinogens (NNAL; polycyclic hydrocarbons) with decreasing nicotine content; 3) No evidence of changes in biomarkers of cardiovascular disease with decreasing nicotine content[4-6]. The mean level of education in participants was college graduation (e.g. ~15-16 years of education) and nearly all subjects were white.

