To determine the modifying effect of menthol on progressive nicotine content reduction and biomarkers: modification effects such as the menthol will be examined by incorporating the menthol-by-group interaction in the multi-variable linear mixed model. The three-way interaction of the menthol-by-group-by-time will be explored but will be removed from the model if not significant. If the menthol-by-group interaction were found significant then mean-profile plot will be used to show the interaction in details.

To determine the predictors of participant drop-out/relapse: it is hypothesized that compensatory smoking behavior as measured by smoking topography and expired carbon monoxide, a higher baseline nicotine dependence behavioral score and rapid nicotine metabolism phenotypes will be associated with drop-out/relapse. The status of drop-out/relapse will be combined with the length of time from randomization to drop-out/relapse or loss of follow-up to form a time-to-event type of variable. Participants who completed the randomization phase of study will be considered as censored records. Kaplan-Meier type analysis (for categorical predictors) or simple Cox proportional hazard regression model (for quantitative predictors) will be used to examine the bivariate associations between the possible predictors and time to drop-out. If a predictor has shown marginal significance (with p-value less than 0.10) in the bivariate analysis then it will be kept in the multiple regression analysis. A multi-variable Cox proportional hazard regression

model will be built to examine the effects of the predictors jointly for time to drop-out. The magnitude and direction of effectiveness will be quantified by the estimated hazard ratios with their 95% confidence intervals. The interaction between the predictors will be explored in the analysis but will be removed if not significant.

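### The pooled menthol-by-group test mixes flavour with control-cigarette strength, because menthol controls received 12.1 or 9.9 mg by enrolment date and non-menthol controls 11.0 mg throughout

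*Combined protocol and SAP*

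**What the plan says.** Section 7.1 sets out two dosing schedules by enrolment date: "Table 1: Dosing Schedule for smokers enrolled in the study prior to 12/19/16" and "Table 2: Dosing Schedule for smokers enrolled 12/19/16 or after". In both, the non-menthol control row is the same: "regular: UNC Around 11mg 11.0 11.0 11.0 11.0 11.0 11.0". The second control row reads "12.1 12.1 12.1 12.1 12.1 12.1" in Table 1 and "9.9 9.9 9.9 9.9 9.9 9.9" in Table 2. The copy reviewed shows no label on that row. The footnote to Table 1 names 12.1 and 9.9 mg as the strengths for menthol control participants who stay on study cigarettes in the Treatment Choice Phase, with the strength "determined by the time of entry into the study due to a 12.1 mg menthol study cigarette supply shortage".

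After randomisation, the reduced-arm steps are identical in the two tables: 7.8, 3.2, 1.3, 0.7 and 0.2 mg for non-menthol, and 7.0, 3.4, 1.4, 0.7 and 0.2 mg for menthol.

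Aim 1b (Section 1.1) expects menthol not to modify the effect of nicotine reduction. Section 9.2 states how this is tested: "modification effects such as the menthol will be examined by incorporating the menthol-by-group interaction in the multi-variable linear mixed model". It names no term for product version, enrolment period or nicotine content. Randomisation (Section 7.4.3) is stratified by site and flavour only.

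**The concern.** A menthol-by-group interaction asks whether the control-minus-reduced difference is the same for the two flavours. Here the control product differs by flavour as well. Menthol controls smoke a cigarette 10% stronger than the non-menthol control (12.1/11.0) or 10% weaker (9.9/11.0), depending on when they enrolled, and none is assigned 11.0 mg. Within each period, strength is fixed by flavour.

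The protocol's own background gives a reason to expect strength to matter, reporting that "Systemic intake of nicotine reflected the nicotine content of the cigarettes, with only small degrees of compensation". A pooled interaction could therefore partly reflect strength, or strength could offset a real menthol effect. Aim 1b predicts no modification and Section 9.2 drops non-significant interactions, so an error in either direction would affect the conclusion.

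**Working it through.** **Inputs.** Contents are from Tables 1 and 2. Cotinine mean (SD) is 240 (120) ng/ml for control and 113 (116) for the reduced arm (Section 9.1). Evaluable sample is 280 (Section 9.1). Assumption: flavours split equally, giving 280/4 = 70 per group-by-menthol cell; the plan's own figure of 70 is per group per race. Two quantities are not in the documents and are varied: p, the share of menthol participants enrolled before 12/19/16, and the content-to-cotinine slope. All calculations are for a single time point without baseline adjustment.

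**Step 1: the plan's own menthol figure.** Section 9.1 claims at least 80% power for 72 ng/ml in pair-wise comparisons of the four cells at alpha 0.0083.
- SD = √[(120² + 116²)/2] = 118.0; SE = 118.0 × √(2/70) = 19.9.
- Power = Φ(72/19.9 − 2.64) = 0.83 (0.82 with SD 120). The figure reproduces.
- It does not describe the interaction. That contrast has SE = √[2 × (120² + 116²)/70] = 28.2. At two-sided 5%, 72 ng/ml has power Φ(72/28.2 − 1.96) = 0.72, and 80% power needs 2.80 × 28.2 = 79 ng/ml. The bias below should be set against the SE of 28.2, not against 72.

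**Step 2: content contrasts, control minus final reduced step.**
- Non-menthol: 11.0 − 0.2 = 10.8 mg.
- Menthol, earlier period: 12.1 − 0.2 = 11.9 mg.
- Menthol, later period: 9.9 − 0.2 = 9.7 mg.

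**Step 3: bias in the pooled interaction.** Mean menthol control content is 9.9 + 2.2p, which differs from 11.0 by 1.1 × (2p − 1) mg. Bias = slope × 1.1 × (2p − 1).
- Line through the plan's two means (assumes 240 applies at 11.0 mg and 113 at 0.2 mg): slope = 127/10.8 = 11.8 ng/ml per mg; maximum bias 12.9.
- Full proportionality: slope = 240/11.0 = 21.8; maximum bias 24.0.

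Rejection rate of a nominal 5% test when menthol has no true effect = 1 − Φ(1.96 − |bias|/28.2) + Φ(−1.96 − |bias|/28.2).

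| p | Bias, line (ng/ml) | Rejection | Bias, proportional (ng/ml) | Rejection |
|---|---|---|---|---|
| 0 or 1 | ±12.9 | 7.4% | ±24.0 | 13.6% |
| 0.25 or 0.75 | ±6.5 | 5.6% | ±12.0 | 7.1% |
| 0.5 | 0 | 5.0% | 0 | 5.0% |

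Proportionality predicts 240 × 0.2/11.0 = 4.4 ng/ml at the last reduced step, against the plan's 113, so it fits the plan's figures less well than the line does.

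**Step 4: precision of a version-specific analysis.** Compare each menthol version with non-menthol participants of the same period, average the two contrasts equally, and assume the same period split in both flavours. Then SE = √{½ × (120² + 116²) × [1/(70p) + 1/(70(1 − p))]}.
- 50:50: 28.2, detectable interaction (2.80 × SE) 79 ng/ml.
- 75:25: 32.6, detectable 91.
- 90:10: 47.0, detectable 132.

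For comparison, the root-mean-square error of the pooled contrast under the larger, proportional bias is √(28.2² + 12.0²) = 30.7 at 75:25. At 90:10 the bias is 24 × 0.8 = 19.2, giving √(28.2² + 19.2²) = 34.1.

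**The case against.** The strongest defence is that the effect is small and the plan already has room for it. The two versions lie symmetrically around 11.0 mg and cancel at an even split. The largest bias needs all menthol participants on one version, an extreme case when the protocol carries two schedules. Section 2.3 notes that compensation limits exposure change at least among higher-nicotine commercial cigarettes, and the contents are nominal, resting on an estimated tobacco weight. Section 9.2 also allows for confounders and effect modifiers. Most of this stands as a limit on size.

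It does not remove the problem. The confounders are unnamed. The data-driven rule requires association with treatment group, which randomisation makes unlikely for product version. A baseline covariate or a version main effect shifts both menthol arms equally and leaves the menthol-by-group contrast unchanged.

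A reader might infer three stronger points that the documents do not support.
- **The supply-shortage footnote shows a control product changing during randomised treatment.** It concerns menthol controls who stay on study cigarettes in the Treatment Choice Phase. In the randomised phase the tables assign strength by enrolment date, constant for each control participant.
- **The randomised comparison is compromised.** Within a flavour, both arms were randomised concurrently, so the reduced-versus-control difference remains valid as an average over versions.
- **A version-by-group model with period-by-group terms should replace the pooled test.** Step 4 shows that its error exceeds that of pooling at 75:25 and 90:10, even under the larger bias.

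**Conclusion.** The mixing of menthol with control strength in Aim 1b is real: it follows from the table rows and the single pooled term, and needs no assumption about cotinine. Its size is not shown by the documents. With 70 per cell, the bias runs from zero at p = 0.5 to about 13 ng/ml on the line through the plan's means, or 24 ng/ml under full proportionality, with both maxima at p = 0 or 1. The 13.6% rejection rate is therefore the outer end of the range and should not be quoted as the expected error. Because p is unstated, a reader cannot tell whether the versions cancel. This calls for a modest addition to the analysis plan, limited to the interpretation of Aim 1b. No view is taken on which product strength is right.

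**What to change.** Keep the pooled menthol-by-group test. Add to Section 9.2 a pre-specified analysis that reports:
- the menthol-by-group contrast separately for the 12.1 mg and 9.9 mg menthol versions, each against non-menthol participants enrolled in the same period;
- the equally weighted average of the two, for which mean menthol control content is (12.1 + 9.9)/2 = 11.0 mg;
- the number of menthol participants on each version.

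State that a pooled interaction, or its absence, will not be attributed to menthol unless the version-specific results agree. Judge agreement from estimates and intervals rather than a test. Even a 48 ng/ml gap between the two menthol controls (21.8 × 2.2 mg, under proportionality) would be detected with only 39% power at 50:50 and 30% at 75:25.

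The change needs only analysis-plan wording, since enrolment date and flavour determine the version. The price is precision: the version-specific intervals are wider than the pooled one, and the averaged one is wider unless the split is even. One limit remains: the early reduced-arm steps also differ slightly by flavour (7.0 against 7.8, 3.4 against 3.2, 1.4 against 1.3 mg), so matching average control content does not isolate menthol completely over the 18 weeks.

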7.2. Study Procedures

7.2.1. Baseline Phase I- Orientation/Assessment Visit and Visit 1 (Day 0)

1. Administer Project Screener 2
2. Informed Consent will be taken in a private clinic room in the CTSI.
 - a. Explain study protocol, use and description of cigarettes, and outcome measures.

Participant (P) will have adequate time to review the consent form and ask any questions. Two consent forms will be signed, one will be left at the clinic and one will be taken with the participant.

3. Give the P the Study Overview Participant Handout (uploaded in Supporting Documents named Study Overview Participant Handout)
4. Give pregnancy test for women childbearing age (have had a period in the past 12 months) and who have not had a hysterectomy for eligibility. Women will give a urine sample and the coordinator will perform a pregnancy urine test to see if it is positive or negative to confirm the eligibility criterion.
5. Complete medical history, NIDA drug screen, and concomitant medications forms and blood pressure measurement will be completed to confirm eligibility (all questionnaires (Q) are uploaded in Supporting Documents section).
6. Research staff will take heart rate (HR), weight, height, and waist:hip ratio measurements. Exhaled CO will be taken by the research coordinator with the Pico+ Smokylzer by blowing into a tube.
7. If P meets all inclusion criteria the coordinator will proceed with the rest of the baseline questionnaires below (all questionnaires are uploaded in Supporting Documents named Appendix of Coordinator entered Surveys and Appendix of Subject entered surveys):
 1. Demographics
 2. Tobacco Use History
 3. Butt out Q.
 4. Cigarette Details
 5. Nicotine Dependence Q.
 6. WI Prepare
 7. Cigarette Liking scales
 8. Revised MN Withdrawal Scale
 9. Questionnaire on Smoking Urges
 10. Centers for Epidemiological Studies (CESD)
 11. Perceived Stress Q.
 12. Kessler 6
5. Explain to P that they will smoke their current brand of cigarettes as usual for the next week. Compliance with the study protocol including not using other forms of tobacco or marijuana will be stressed. Participants will also be asked to honestly report any other tobacco or marijuana use at subsequent visits.
6. The study coordinator will give out and explain to P how to fill out the daily cigarette diary (in Supporting Documents section). They will be instructed to use this every day to tally their cigarettes smoked. They will also be asked to circle in their diary any non-research cigarettes that they smoke so that we can record this at subsequent visits.
7. A subset of 100 P (50 each arm) will be asked to provide 4 saliva samples throughout the course of the day before they come into the next clinic visit to look at Cortisol (stress biomarker). They will be given a kit with instructions on collection and will watch an instructional how-to video (uploaded in Supporting Documents). To collect a saliva sample Ps will place a cotton swab under their tongue for 2 minutes. They will repeat this 4 more times throughout the day. Ps will be asked to complete a cortisol log on the day they take the cortisol saliva samples. The log will be provided in the kit with the collection tubes. It will provide instructions on how to take the samples along with dates and times for each sample that was collected. Additional questions in the log address possible interactions with cortisol such as, stress events, alcohol consumption, and exercise. Once they are done collecting the samples for the day they will keep them in the refrigerator until it is time to bring them to the clinic visit the next day.
8. A randomly selected subset of 100 Ps will be asked to use the Smoking Puff Analyser-Mobile (SPA-M) (SODIM, France) smoking topography device which mechanically records measures of smoking (e.g. number of puffs, puff velocity, puff duration, interpuff interval, puff volume) for baseline topography assessment. The P will smoke through a

plastic mouthpiece connected by a plastic tube to a handheld, portable device with a pressure transducer. Ps will be instructed on how to use the device and will be given an instructional handout for reference. They will also watch an instructional how-to video (uploaded in Supporting Documents). They will be asked to smoke all of their cigarettes as they normally do with the device for next two days after the visit. Participants who are selected to use the device will collect cigarette butts for one day while using the device and collect cigarette butts from one day while not using the device. Instructions (uploaded in Supporting Documents) and storage bags to collect the butts will be given. They will bring the butts back at their next visit.

9. The next study visit will be scheduled for one week later at approximately the same time. They will receive a print out of their next study visits and phone calls.

